The study is designed to detect an improvement in the percentage responding compared with a historical percentage of 40%. The study will enroll a target of 120 subjects to ensure collection of sufficient efficacy and safety data. The study will have 80% power to detect a 13% increase in the percentage responding from 40% to 53%, 90% power to detect a 15% increase from 40% to 55%, and 95% power to detect a 17% increase from 40% to 57%, at 1-sided 2.5% significance level. Calculations used PASS 2019, v19.0.2.

The justification for the performance goal of 40% comes from published literature for the approved and thought to be clinically significant third-line device for UUI—a fully-implanted neuromodulation device called “Interstim”. Note that given this study’s sample size, to observe 50% of patients improve by at least 50% in their urgency urinary incontinence symptoms as measured at the 12 month point, the lower bound

Pivotal Study of Subcutaneous Tibial Nerve Stimulation with eCoin[®] for Urgency Urinary Incontinence.

of a 95% confidence interval is 40%. The published literature on sacral neuromodulation supports the clinical significance of a 40% responder rate. From the observed modified ITT responder rate in the well-cited ROSETTA study (38), it can be deduced that there is a lower bound of 41% for those with diaries for all 6 months, and 43% for those with at least 4 months of diaries. Importantly, these results are not ITT. In the review of the Insite study (39), the Sponsor derived an ITT responder rate of 59% from the available as-treated analyses. From this ITT deduction, the lower bound of the 95% confidence interval is 44%. Both of these published data were measured at 6 months whereas the endpoint in the study contemplated by this IDE is 12 months. If either study was extended to 12 months, the number of subjects reporting would likely be even smaller, resulting in a lower bound at or below 40%.

39. Siegel, Steven, et al. "Results of a prospective, randomized, multicenter study evaluating sacral neuromodulation with InterStim therapy compared to standard medical therapy at 6-months in subjects with mild symptoms of overactive bladder." *Neurourology and Urodynamics* 34.3 (2015): 224-230.

3-9-5 Calculation of Effectiveness Variables

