5.7. Long-term completers

The long-term completers population will consist of all mITT subjects who attend a particular visit. This is the primary analysis population for the effectiveness and safety analyses performed at 2 and 3 years post-activation for subjects who consent to extended follow-up.

6. Sample size consideration

The study protocol specifies enrollment of up to 135 subjects, with a target of 120 subjects. The study is designed to estimate the proportion of responders. A responder is a subject who achieves a clinically meaningful level of improvement, defined as having at least a 50% improvement in the number of UUI episodes per 24 hours on a 3-day voiding diary after 48 weeks of therapy.

The performance goal for this study is to show at least a 40% response rate after 48 weeks of therapy. The primary efficacy analysis will be performed by testing the null hypothesis H_0 that the percentage responding is less than or equal to 40% against the alternative hypothesis H_1 that the percentage is greater than 40%. The test will be performed at an overall 1-sided 2.5% level of significance.

H_0 : the true percentage responding $\leq 40\%$

H_1 : the true percentage responding $> 40\%$

The study will be considered successful if the lower bound of the 2-sided 95% exact Clopper-Pearson confidence interval for the percentage responding is greater than 40%.

The study is designed to detect an improvement in the percentage responding compared with a historical percentage of 40%. The study will enroll a target of 120 subjects to ensure collection of sufficient efficacy and safety data. The study will have 80% power to detect a 13% increase in the percentage responding from 40% to 53%, 90% power to detect a 15% increase from 40%

to 55%, and 95% power to detect a 17% increase from 40% to 57%, at a 1-sided 2.5% significance level. Calculations were performed using PASS 2019, v19.0.2.

For illustration purposes, the table below shows 95% confidence intervals for various observed proportions of responders, assuming a sample size of 120. An observed proportion of responders of at least 0.50 will give a lower bound of the 2-sided 95% exact Clopper-Pearson confidence interval slightly above 0.40.

Table 2. Confidence intervals by observed proportion of responders

Sample size=120	Observed proportion of responders					
	0.5	0.55	0.6	0.7	0.8	0.9
	(0.41, 0.59)	(0.46, 0.64)	(0.51, 0.69)	(0.61, 0.78)	(0.72, 0.87)	(0.83, 0.95)

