- Any subject explanted, except for those explanted for an MRI, prior to 48 weeks post-activation will be imputed as a non-responder (meaning the subject will be imputed as having not achieved at least a 50% reduction from baseline in the number of UUI episodes).
- Subjects who are explanted for an MRI will have data post-MRI imputed. These imputed data for the primary effectiveness outcome variable will be assumed missing at random and will be handled with multiple imputation. See Section 13.2 for further details and example SAS code.
- Any subject for whom 48 week post-activation data are unavailable and the study investigator does not know whether the device has been explanted will be assumed to be a non-responder.
- Subjects for whom 48 week post-activation data are unavailable but the device is known not to have been explanted will have their missing data imputed. The missing data for the primary effectiveness outcome variable will be assumed missing at random and will be handled with multiple imputation. See Section 13.2 for further details and example SAS code.
- Any subject who undergoes a procedure for implantation of eCoin™, whether or not the device is activated, will be treated as if they were activated.

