13.2. Missing data for primary efficacy outcome

The primary efficacy analysis is based on the proportion of responders at 48 weeks post-activation. Subjects for whom 48 week post-activation data are unavailable but the device is known not to have been explanted or subjects who have been explanted for an MRI will have the primary endpoint data imputed. The missing data for the primary effectiveness outcome variable will be assumed missing at random and will be handled with multiple imputation.

The multiple imputation procedure will use fully conditional specification (FCS) and create 100 imputed datasets. The type of model used for FCS will depend on the variable with missing outcome data. Continuous variables will use regression with predictive mean matching; ordinal and nominal classification variables will use response logistic regression. All variables will be assessed for collinearity before inclusion in the multiple imputation model. Table 3 lists the variables with descriptions that will be used in the model.

The imputation will follow the sample SAS version 9.4 code provided in Exhibit 2. The SAS code may be modified slightly as needed according to software updates and compatibility with actual data. For example, the order of the variables in the VAR statement of the PROC MI procedure will be adjusted to approach monotone missingness. The variables are imputed sequentially in the order specified in the VAR statement with FCS.

The 100 complete datasets created by multiple imputation will be analyzed separately by imputation. The SAS PROC MIANALYZE procedure will be used to combine results from the 100 analyses.

Table 3. Variables in the multiple imputation model

Type	Variable	Description
Binary	SEX	Sex
Continuous	AGE	Age
Continuous	BMI	BMI at baseline
Binary	TENSR	Response to the TENS protocol
Continuous	BASE_OABQ	Baseline OABq total score
Continuous	OABQ4	Week 4 OABq total score
Continuous	OABQ8	Week 8 OABq total score
Continuous	OABQ12	Week 12 OABq total score
Continuous	OABQ24	Week 24 OABq total score
Continuous	OABQ36	Week 36 OABq total score
Continuous	OABQ48	Week 48 OABq total score
Ordinal	PGI4	Week 4 PGI-I questionnaire score
Ordinal	PGI8	Week 8 PGI-I questionnaire score
Ordinal	PGI12	Week 12 PGI-I questionnaire score
Ordinal	PGI24	Week 24 PGI-I questionnaire score
Ordinal	PGI36	Week 36 PGI-I questionnaire score
Ordinal	PGI48	Week 48 PGI-I questionnaire score

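### Minor: at the target of 120 subjects the exact success rule gives 77% power at 53% and 88% at 55%, not the stated 80% and 90%; the 95% at 57% is right to rounding

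*SAP*

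**What the plan says.** SAP section 6 and Protocol 3-9-4 set a performance goal of 40% responders at 48 weeks. On the error rate the SAP says: "The test will be performed at an overall 1-sided 2.5% level of significance". The trial is to be judged "successful if the lower bound of the 2-sided 95% exact Clopper-Pearson confidence interval for the percentage responding is greater than 40" percent. On size: "The study will enroll a target of 120 subjects to ensure collection of sufficient efficacy and safety data"; the cap is 135.

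The power claim reads: "The study will have 80% power to detect a 13% increase in the percentage responding from 40% to 53" percent. It continues with "90% power to detect a 15% increase from 40% to 55" percent, and then 95% power at 57%. The only statement of method is the software: "Calculations were performed using PASS 2019, v19.0.2". Neither document says whether an exact or an approximate test was selected, or whether the program was asked for power or for a detectable rate.

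Directly after this, SAP Table 2 shows confidence intervals for 120 subjects, and the SAP notes that an observed proportion of 0.50 is enough to put the lower bound just above 0.40.

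**The concern.** The power sentence should describe the success rule that stands beside it, at the sample size that it names. An exact binomial rule moves in whole subjects, so its power rises and falls in steps as the sample size changes. At 120 subjects the attained one-sided error is well below 2.5%, and some power is lost with it. A reader who recomputes power from the stated rule at the stated target does not get the first two printed figures.

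This is the stated power of the trial's only hypothesis test, so it should be reproducible. If it is overstated, the chance of missing the goal when the device performs as assumed is understated.

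**Working it through.** **Inputs** (SAP section 6; the same in Protocol 3-9-4): n = 120, p0 = 0.40, one-sided alpha 0.025, success if the Clopper-Pearson lower bound exceeds 0.40, and alternatives p1 = 0.53, 0.55, 0.57 with stated power 80%, 90%, 95%. It is assumed that every outcome is either observed or set to non-response.

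**1. Reproducing the plan's figures.** Two routes come close.

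*Route A: normal approximation with null standard error and continuity correction.*

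Power = Φ{ [p1 − p0 − 0.5/n − 1.96·√(p0(1−p0)/n)] / √(p1(1−p1)/n) }

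Here √(0.24/120) = 0.04472, 1.96 × 0.04472 = 0.08765, and 0.5/120 = 0.00417.

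- p1 = 0.53: (0.13 − 0.00417 − 0.08765)/0.04556 = 0.838, power 79.9%
- p1 = 0.55: (0.15 − 0.00417 − 0.08765)/0.04541 = 1.281, power 90.0%
- p1 = 0.57: (0.17 − 0.00417 − 0.08765)/0.04519 = 1.730, power 95.8%

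Without the correction the results are 82.4%, 91.5% and 96.6%.

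*Route B: exact rule solved for the detectable rate.* Solving P(X ≥ 60 | 120, p) = 0.80, 0.90, 0.95 gives p = 53.41%, 55.41%, 57.04%. These round to the printed 53, 55 and 57.

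**2. The success threshold.** The lower bound for x responders is the 2.5% quantile of Beta(x, n − x + 1).

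- 59/120: 0.3993, fail; P(X ≥ 59 | 120, 0.40) = 0.0260
- 60/120: 0.4074, pass; P(X ≥ 60 | 120, 0.40) = 0.0167

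So 60 responders are needed, which agrees with the SAP's remark about 0.50, and the attained one-sided alpha is 1.67%.

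**3. Exact power under the stated rule**, P(X ≥ 60 | 120, p1):

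| True rate | Stated | Exact | Gap (points) |
|---|---|---|---|
| 53% | 80% | 77.35% | 2.65 |
| 55% | 90% | 88.33% | 1.67 |
| 57% | 95% | 94.91% | 0.09 |

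**4. Dependence on n.** The threshold is recomputed for each size.

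| n | Responders needed | 53% | 55% | 57% |
|---|---|---|---|---|
| 119 | 59 | 79.95% | 89.96% | 95.74% |
| 120 | 60 | 77.35% | 88.33% | 94.91% |
| 121 | 60 | 80.06% | 90.09% | 95.84% |
| 135 | 66 | 85.16% | 93.46% | 97.63% |

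Every n from 121 to 135 meets all three stated powers; the lowest values in that range are those at 121.

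**5. Which method the SAP uses nearby.** All six intervals in Table 2 are exact Clopper-Pearson intervals at 120. For example, 96/120 gives 0.717 to 0.867, printed as 0.72 and 0.87; a Wald lower limit would be 0.728 and would print as 0.73. The exact method is therefore already in use, at this sample size, next to the power sentence.

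**The case against.** The strongest reply is that the sentence may report rounded detectable rates. It pairs conventional powers of 80%, 90% and 95% with whole-number increases, as a minimum-detectable-effect calculation often does. The exact rates of 53.41%, 55.41% and 57.04% round to all three printed values, while the continuity-corrected approximation gives 95.8% at 57%, which would print as 96%. On that reading nobody made an arithmetic error, and 53.4% was simply printed as 53%. This is plausible and may well be the origin. It explains the sentence without making it true: as printed it claims 80% power at 53%, and the rule gives 77.4%. Because the PASS procedure is not named, the reader cannot tell which account applies.

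A second reply is that 120 is an unlucky step. That is correct: 121 subjects need the same 60 responders and meet all three figures, and the plan allows up to 135. But 120 is the declared target and the size used in Table 2.

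Third, little depends on the sentence now. The SAP is dated August 2019 and the protocol expected enrolment to finish by March 2019, so on that timetable it no longer guides a sample-size decision. This is a good reason to grade the point as minor.

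Fourth, an exact figure is also only a planning value, since some missing outcomes are multiply imputed. SAP 10.1 says: "The missing data for the primary effectiveness outcome variable will be assumed missing at random and will be handled with multiple imputation"; and SAP 13.2 says: "The SAS PROC MIANALYZE procedure will be used to combine results from the 100 analyses". The 60-responder cutoff does not apply directly to a pooled analysis. This stands as a limit, and the replacement text should state it.

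**Conclusion.** The point holds, as a minor one. At 120 subjects the pre-specified rule gives power of 77.4%, 88.3% and 94.9% at true rates of 53%, 55% and 57%. The stated 80% is 2.65 points too high, the stated 90% is 1.67 points too high, and the stated 95% is correct to rounding. At a true rate of 53% the chance of missing the goal is 22.7% rather than 20%. Taken alone, the gap at 55% is modest; the gap at 53% is the clearer discrepancy.

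Type I error is not inflated, and neither the success rule nor the analysis is affected. The result assumes exactly 120 subjects in the analysis and no multiply imputed outcomes. How the printed figures were obtained remains unknown.

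**What to change.** In SAP section 6 and Protocol 3-9-4, replace the power sentence with text such as:

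> With 120 subjects and the exact Clopper-Pearson rule, power is 77%, 88% and 95% at true rates of 53%, 55% and 57% (equivalently, 80%, 90% and 95% power at 53.4%, 55.4% and 57.0%); attained one-sided alpha is 1.7%. Calculations assume no multiply imputed outcomes.

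Also name the PASS procedure and test option that were used. Giving both power at the stated rates and rates at the stated power serves the sponsor whichever way the printed figures arose.

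The cost is one sentence in each of two documents and a slightly less favourable power statement. No patients are added, and the success rule and analysis do not change.

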7.1. Study days

For the purpose of the analysis, study day will be calculated relative to device implantation or initial activation, depending on the analysis:

- Study day relative to implantation = date of visit/test – implantation date + 1.
- Study day relative to activation = date of visit/test – activation date + 1.

If the date of visit/test occurs before the date of interest, then study day = date of visit/test – implantation/activation date. Day 0 will not exist.

7.2. Baseline

Baseline efficacy measures will be defined as the last measure taken up to and including the baseline visit (Visit 2). Baseline safety measures will be defined as the last measure taken prior to device implantation.

7.3. Changes to planned analyses

Changes to the analyses described in this plan will be fully documented in a revised version of the plan written prior to locking the study database and conducting the primary outcome

analysis. Changes made after locking the study database will be described in the clinical study report and characterized as “exploratory”.

8. Study population summaries

8.1. Subject disposition

The number and percentage of subjects who fall into each of the following categories will be presented:

- Total enrolled
- Total enrolled subjects who undergo a procedure for implantation of eCoin™ (the ITT population)
- Total implanted with eCoin™
- Subjects in the ITT population meeting all eligibility criteria (the mITT population)
- Implanted subjects with the device activated
- OAB drug-free population
- Per-protocol population
- Responders population
- TENS cohort analysis population
- Early termination from the study
- Long-term completers
- Completed study

For subjects who withdraw from study early, the number and percentage withdrawing by reason will also be presented. The eCoin™ device must be recommended to be explanted if an early termination occurs.

A by-subject listing of early terminations will also be presented, including study day and the reason for early termination.

8.2. Eligibility and protocol deviations

Inclusion and exclusion criteria not met at screening (screen failures) will be presented for all screened but not enrolled subjects. Eligibility criteria not met for enrolled subjects will also be presented.

Protocol deviations are collected throughout the study and will be summarized. A major protocol deviation is defined as one that affects the safety of the subject or the scientific validity of the results. A minor deviation is defined as one that does not affect the safety of the subject or the scientific validity of the results.

The following are examples of minor protocol deviations:

- Use of OAB medications
- Follow-up visits that occurred outside the protocol required time frame because of the participant's schedule
- Study procedure conducted out of timeframe
- Participant failure to initial every page of the consent form
- Participant failure to return the patient diary
- Copy of the informed consent form not given to the participant
- Missing original signed consent, but a copy exists
- Patient not given implant card

8.3. Demographics and baseline characteristics

Demographic and baseline characteristics will be summarized by age, gender, ethnicity, race, current smoker, and any abnormal findings from a complete physical exam.

Age in years will be calculated as the integer portion of the following:

$$[(\text{Date of enrollment} - \text{Date of birth}) + 1] / 365.25$$

Percentages will be calculated relative to the number of subjects enrolled.

OAB history will be presented. It will include duration of OAB and success of prior treatments (PTNS therapy, TENS therapy, OAB medications, and Botox). Success will be categorized as “yes”, “no”, or “short-term/partial response.”

Medical history will be coded using the Medical Dictionary for Regulatory Activities (MedDRA) and will be summarized by system organ class (SOC) and preferred term (PT).

Prior medications, defined as medications started prior to device implantation, will be presented by their drug generic names, as reported on the prior medication case report form (CRF). The number and percentage of subjects who took at least one drug within each generic type will be presented. Prior medications will be presented separately for OAB and non-OAB medications.

8.4. Treatment exposure

Duration of device implantation and device activation, in weeks, will be summarized for all enrolled subjects.

8.5. Concomitant therapy

A concomitant therapy is defined as therapy (other than eCoin™) started on or after implantation. A therapy taken prior to implantation is not considered a concomitant therapy. If a subject stops taking or changes the dosage of a medication recorded in the medical history at screening, or begins taking a new medication, then this medication will be included as a concomitant medication. Information on concomitant medications will be summarized by generic name as reported on the concomitant medication CRF.

The number and percentage of subjects who took at least one drug within each generic type will be presented. Concomitant medications will be presented separately for OAB and non-OAB medications.

9. Follow-up assessments

9.1. 3-day voiding diary assessments

Throughout the study, subjects will complete 3-day voiding diaries to quantify voiding behavior, symptoms, and incontinence. The diary should be completed over three consecutive days during the seven days prior to each visit involving a 3-day diary. The site should telephone subjects to remind them of the diary requirement at least three days prior to each visit. The voiding diaries will collect the following information per 24 hours over 3 days:

- total number of daytime voids (6:01 a.m. – 9:59 p.m.)
- total number of night voids (10:00 p.m. – 6:00 a.m.)
- total number of voids
- total amount voided
- total number of toilet urgent episodes
- total number of leaks
- total amount leaked
- total number of urge leaks

The voiding diary CRF will report the total over the three days for each measure, which will then be averaged. All efforts will be made to ensure that all diaries are completed over the full three day period. Any incomplete diaries will be reported and averaged over the total days in which they were completed.

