2.5. Eligibility criteria

See the protocol for eligibility criteria.

After enrollment for this study began, Valencia discovered that one center had implanted the eCoin™ neuromodulation device in several subjects who had not met the eligibility criteria. Valencia will implement further on-site training in an effort to prevent any additional subjects from being consented and enrolled in the study without meeting all eligibility criteria. Any subjects enrolled who do not meet all eligibility criteria where the eligibility violations are mendable and found prior to device activation (e.g. missing a test at screening or not being washed off of pharmacological treatment of overactive bladder for at least two weeks prior to baseline) will be re-baselined. Subjects enrolled who do not meet eligibility criteria will still be included in the safety and efficacy analyses.

3. Study objectives and outcome measures

The G170301 study is designed to evaluate the safety and efficacy of eCoin™ tibial nerve stimulation in subjects with UUI. See Table 1 for the study objectives and outcome measures. The primary outcomes will be measured after 48 weeks of eCoin™ therapy (equivalent to 52 weeks post-implantation). The secondary outcomes will be measured at 24 weeks of eCoin™ therapy (equivalent to 28 weeks post-implantation). The primary and secondary efficacy outcome measures will be based on data collected from 3-day voiding diaries. The diaries should be completed over three consecutive days during the seven days prior to each visit. Accordingly, the primary efficacy outcome measured at the post-activation week 48 visit will be based on voiding diary data collected within 7 days prior to the week 48 visit.

Table 1. Study objectives and outcome measures

Primary effectiveness
Objective: to assess the effectiveness of eCoin™ on the proportion of responders, that is, subjects achieving at least a 50% improvement in the number of UUI episodes per 24 hours on a 3-day voiding diary after 48 weeks of therapy
Assessment of outcome: proportion of responders after 48 weeks of therapy

Key secondary effectiveness
Objective: to assess the effectiveness of eCoin™ on the proportion of responders, that is, subjects achieving at least a 50% improvement in the number of UUI episodes per 24 hours on a 3-day voiding diary after 24 weeks of therapy
Assessment of outcome: proportion of responders after 24 weeks of therapy

Primary safety

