10.4.2. Additional OAB medications

Medications for OAB are not allowed until the primary effectiveness endpoint is reached at 48 weeks post-activation, unless judged medically necessary. Any subjects who have taken OAB medications will be included in the primary effectiveness outcome variable analysis. OAB medication use will be reported alongside the primary analysis. The timing of OAB medications will be displayed, including duration of treatment, start and end dates, and dosage.

The following additional sensitivity analyses may be performed.

- For the primary effectiveness outcome variable at week 48, data for subjects who have taken OAB medications while on study will be considered missing and imputed assuming they had not taken any OAB medication.
- For weeks 4, 8, 12, 24, 36, and 48, 2 different sets of analyses will be performed.
 - *While on OAB medication.* Subjects will be imputed as non-responders while they are taking OAB medication.
 - *Any OAB medication.* A very conservative set of analyses will consider a subject a non-responder at every visit after she starts OAB medication.

For example, no matter what subjects write on their diaries, the “while on OAB medication” analyses will consider subjects as non-responders from week 12 through week 36 if they take OAB medication at week 12 and stop that medication at week 36. The “any OAB medication” analyses will consider such subjects non-responders from week 12 through week 48.

11. Safety summaries

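### SAP 8.5 misclassifies on-study medication use: it leaves out a drug continued unchanged through implantation and counts one stopped at screening

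*SAP*

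**What the plan says.** SAP 8.5 contains three statements about what counts.

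1. Base rule: "A concomitant therapy is defined as therapy (other than eCoin™) started on or after implantation".
2. Exclusion: "A therapy taken prior to implantation is not considered a concomitant therapy".
3. Inclusion: "If a subject stops taking or changes the dosage of a medication recorded in the medical history at screening", or starts a new one, that medication is counted as concomitant.

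The result is "summarized by generic name as reported on the concomitant medication CRF", with OAB and non-OAB drugs shown separately.

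SAP 8.3 covers the other side: "Prior medications, defined as medications started prior to device implantation", with no condition that the drug was stopped. It also says: "Prior medications will be presented separately for OAB and non-OAB medications".

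SAP 10.4.2 keeps subjects who took OAB drugs in the primary analysis and says: "OAB medication use will be reported alongside the primary analysis". That display is to show duration, dates and dosage. SAP 5.3 defines the OAB drug-free set as mITT subjects with no OAB medication in the study period. Neither section refers to 8.5.

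Protocol 3-4-2 starts the two-week wash-off at Visit 1. Protocol 3-4-12 has subjects asked about OAB medication at every follow-up visit, with a positive answer entered on the visit CRF and on a concomitant medication CRF.

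**The concern.** A table of concomitant use should show who was taking what while the device was in place. The 8.5 rule turns instead on when a drug was started and whether it was altered. A subject who takes an OAB drug unchanged from screening to week 48 appears only as a prior-medication user. A subject who stopped at Visit 1, as the protocol requires, meets the inclusion clause.

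This is a single-arm, open-label trial judged against a fixed 40% responder goal, and subjects on OAB drugs stay in the primary analysis. The reader therefore depends on the medication displays to judge how far drug use may have contributed to response. The 8.3 table cannot repair the gap. It counts by generic name on start date alone, so a drug stopped before baseline and one taken through week 48 look the same there.

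Section 8.5 is also the SAP's only definition of on-study medication use. Section 10.4.2 does not name the records that identify users, and 5.3 does not define the study period. A programmer could reasonably carry the 8.5 rule into either section.

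**Working it through.** There is no planned figure to reproduce. The check applies the three statements of SAP 8.5 to the possible patterns of OAB drug use.

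| Pattern | Taken on or after implantation? | Base rule | Exclusion | Inclusion clause |
|---|---|---|---|---|
| A. On drug at screening, washed off at Visit 1, never resumed | No | Out | Out | **In** (stopped) |
| B. On drug at screening, never stopped, same dose through follow-up | Yes | Out | Out | Does not apply |
| C. Washed off, resumed between baseline and implantation, continued | Yes | Out | Out | In (stopped) |
| D. First started between baseline and implantation, continued | Yes | Out | Out | Arguably in (new drug) |
| E. First started after implantation | Yes | In | Not triggered | In |

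Only E is classified correctly and without conflict. B is wrong under every statement. A is wrong if the inclusion clause governs. C and D are wrong if the exclusion sentence governs, and the text does not say which prevails.

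Patterns C and D are possible for eligible subjects. Inclusion criterion 7 concerns the time before baseline, and protocol 3-4-2 puts implantation 7 to 35 days after baseline (3-4-8 says no later than 28 days; the two need reconciling, but a gap exists under either).

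**Direction of the error.** For the 8.5 OAB table, let

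- s = subjects who start an OAB drug after implantation,
- w = subjects counted only because a screening OAB drug was stopped (A),
- c = subjects on an OAB drug started before implantation and left out (B, and C or D if the exclusion sentence is applied to them).

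Literal count = s + w. Actual on-study use = s + c. Error = (s + w) − (s + c) = w − c.

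The documents give none of these numbers. With assumed values, N = 120, s = 10, w from 24 to 72 (20% to 60% of 120) and c from 0 to 10:

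- literal count: 10 + 24 = 34 to 10 + 72 = 82;
- actual use: 10 + 0 = 10 to 10 + 10 = 20;
- error: 24 − 10 = +14 to 72 − 0 = +72, an overstatement.

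If the exclusion sentence governs, washed-off drugs stay out, w = 0 and the error is −c: from 0 to −10 here, and 0 if washout was fully observed and nothing was resumed or started before implantation. The same text can therefore overstate or understate use.

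**The case against.** The strongest reply is that this is loose drafting in a descriptive table and nothing that matters depends on it. Much of that stands.

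- **The report beside the primary result.** A reader might infer that OAB use shown there is understated. The documents do not support this. SAP 10.4.2 and protocol 3-9-7-1 cover all subjects who took OAB drugs, with dates and dosage, and do not limit the display to concomitant drugs as 8.5 defines them. Protocol 3-4-12 captures use at each follow-up visit whatever the start date, so a continuing user should have a record.
- **The ineligible implanted subjects.** A reader might take SAP 2.5 as saying that subjects still on OAB drugs were implanted. It says that several subjects at one center did not meet the criteria, without saying which criteria. The phrase "not being washed off of pharmacological treatment of overactive bladder for at least two weeks prior to baseline" is only an example of a violation that can be mended. No continuing user is documented.
- **The analysis sets.** An uncorrected washout failure is ineligible, so it falls outside mITT and hence outside the drug-free and per-protocol sets, whatever 8.5 says.
- **The degree of confounding.** A drug taken unchanged at baseline and at week 48 is in both diaries. A drug begun or resumed after the baseline diary distorts the change from baseline more.
- **The pass/fail margin.** One subject in 120 is 1/120 = 0.83 points, and the exact lower limit moves from 0.3993 at 59 responders to 0.4074 at 60. These figures do not apply: the ITT analysis includes OAB drug users under any definition, so reclassifying a drug changes no responder.

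The reply does not remove the defect in 8.5 itself. Capture on the CRF does not help if the SAP definition then tells the programmer to set the record aside. Washout makes pattern B rare but makes pattern A the expected course for anyone on an OAB drug at screening.

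**Conclusion.** SAP 8.5 is wrong as written. It omits a drug continued unchanged through implantation, can count one that was correctly washed off, and contradicts itself for other drugs taken before implantation. The concomitant OAB table will be misstated by w − c whenever those counts differ. Neither its size nor its direction can be fixed from the documents, and the ranges shown rest on assumed counts.

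The effect is confined to descriptive tables and possibly to who is classed as an OAB user in the drug-free set and in the 10.4.2 sensitivity analyses, which are themselves optional. That second effect arises only if 8.5 is applied there, which the text neither requires nor rules out. The ITT responder count and the success decision are unaffected.

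**What to change.** Replace the 8.5 definition with one based on use: a concomitant medication is any medication taken on or after the implantation date, whatever its start date. State that a drug may be both prior and concomitant, and that one stopped before implantation and not resumed is prior only. Delete the exclusion sentence and the stop-or-change clause as tests of concomitance.

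Add to SAP 5.3 and 10.4.2 that OAB use is identified from the OAB medication answer on each follow-up visit CRF together with the start and stop dates on the medication CRF. In 5.3, give the start and end of the study period.

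The cost is SAP wording, to be changed before database lock as SAP 7.3 provides. The data are already collected under protocol 3-4-12, and no new visit, form or sample size is needed.
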